#### **Deviation from standard treatment**

The time from adenoma resection to follow-up colonoscopy in case of high-risk adenomas was in Denmark 1 year and for piecemeal resection for 3 months control colonoscopy and after 12 months for full colonoscopy. This has been changed per May 1, 2023 to: for piecemeal resection-at 6 months a control colonoscopy and afterwards a full colonoscopy at 18 months and for en-bloc resection a full colonoscopy at 18 months. In Sweden, the period is 1-3 years depending on the type of high-risk adenomas. In this study piecemeal resection patients are invited at a 3 month control colonoscopy and they are all invited for full colonoscopy after one

year. This means that patients will have an earlier follow up. This regimen is compliant with international guidelines in many European countries.

# Risks disadvantages and side effects.

The risks are considered low. Few patients will have a control colonoscopy earlier by 3 months (as was the standard procedure until May 2023). The clinical guidelines for a follow up colonoscopy has been after 1 year in Denmark until May 2023. As European, British and American as well as Swedish guidelines offer a 1-3 year follow up there will be no risk for the patient to have the follow up after 1 year.

Carrot juice are considered health promoting for several reasons, and any toxic dose cannot be obtained with the amounts delivered. Discoloration of skin might be seen I cases who take higher doses than recommended. The placebo juice is produced by commercially available juice and taste additives (ginger). The calories contained in both products might theoretically give a low gain of body weight.

# Data collection, management and analysis

Data will be collected after informed consent will be obtained. Patients will be informed that researchers involved in the project will have access to their data and in need (control or inspection purposes), sponsors and regulatory authorities will have access to our database.

The consent provides the responsible researcher, sponsor, investigator, and their representatives, as well as any regulatory authority, direct access to obtain information in the patient's medical records, including electronic records, for the purpose of reviewing information related to the subject's health status that is necessary for the conduct of the research project and for monitoring purposes, including self-monitoring, quality control, and monitoring tasks that they are obligated to perform.

Data collection will be performed by dedicated research staff. Data will be collected and entered into the electronic database REDCap via OPEN at OUH. We will enter data from the questionnaire, patient journal, pathology answer etc.

### Information collected from patient files and questionnaires:

From the patient file: Quality and technical details of both colonoscopy, allergies, former colonoscopies and polypectomies and the pathology report on adenomas resected. Only data necessary to answer the described aims will be collected.

We will not need to give patient information to others to recruit patients. The patients will be invited to participate if they have a polyp bigger than 20 mm regardless of other information from the patient journal which we will not access at this timeline. Patient information will not be collected at the inclusion but will be accessed by research responsible and entered into a RedCap database after the patient will be already included in the project. Only project members have access to data and data will be destroyed after analysis. The project will be registered in the Data Protection Agency. The data protection law and regulations will be obeyed including the chapter V.

Data obtained in Sweden will be entered into the Danish RedCap database in OPEN directly after a data sharing agreement has been lawfully obtained between the sites. After the completion of the database all data will be pseudoananomized. Data will be destroyed after publication of the results from the 3-year colonoscopy, or – if scientifically useful, prolongation until the 5-year colonoscopy will be applied for.

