### Project description for a human trial on colorectal cancer prophylaxis:

#### Aim:

Primary aim:

To investigate for a possible inhibitory effect from carrot juice on the recurrence of excised adenomas and, on the formation of metachronous adenomas in patients who are enrolled in a follow up program after resection of high risk colorectal adenomas.

An inhibitory effect of carrot juice will be measured by a combined endpoint of total number of recurrent adenomas multiplied with mean size of recurrent adenomas in the active arm or the placebo group. This difference will be significant if carrots mediate a 20% reduction in both size and numbers.

If the difference in number of polyps is 40 % or more, we will be able to prove this to be significant. If the difference in polyp size is larger than 40 % we will also achieve statistical difference between the 2 groups.

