### **Inclusion criteria**

1. The patient has adenomas larger than 20 mm in size

2. The patient is willing to accept the treatment and follow-up program for1 year.

3. The patient is capable to understand and follow the instructions. The patient gives written informed consent.

Patients meeting the following exclusion criteria will be excluded from the study:

- 1. Patients allocated to "high-risk" group because of many small polyps (>4).
- 2. Mental illnesses or suspected significant compliance challenges.
- 3. Pregnancy.
- 4. Known allergy to carrots.

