### Scenario 2 - Resection at second visit:

Finding and not removing high-risk polyp at initial colonoscopy, following a referral to specialized unit for later removal.

At the first colonoscopy polyp (s) are identified that need referral to EMR/ESD. Patients are informed about the project and informed consent and written info are handed out. All information will be given along with information about the finding from the colonoscopy according to national guidelines in privacy by the endoscopist or the specialized nurse (in a private room with close d doors to ensure patient confidentiality). The patient is informed that he/she has the right to have a person of his own choice to

participate.. When they come back to the specialized unit for resection, earliest 48 hours after the first colonoscopy, the patient will bring the informed consent signed if he wants to participate in the study or if he/she has further questions or needs another person to be present at the discussion, the project nurse will answer the questions and furthermore instruct the patients. If the patients agrees entering the study, they will be handed out 8 liters of carrot juice, diary and questionnaire.

For further information about the recruitment scenarios, see attachment "patient flow".

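### Criterion 1 requires an adenoma over 20 mm, but patients are invited on any polyp over 20 mm and can be enrolled before the index pathology is read

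*Protocol*

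**What the plan says.** All references are to the protocol.

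- **Inclusion criteria**, item 1: "The patient has adenomas larger than 20 mm in size". The exclusion list names neither cancer nor non-adenoma histology.
- **Aim**: the population is patients in follow-up "after resection of high risk colorectal adenomas". Task 1.4, Design of the intervention and Patient recruitment also describe it by high-risk adenomas.
- **Information collected from patient files and questionnaires**: "The patients will be invited to participate if they have a polyp bigger than 20 mm regardless of other information". The sentence goes on to specify information in the patient journal, which is not to be opened at that stage. The next sentence reads "Patient information will not be collected at the inclusion but will be accessed by research responsible and entered into a RedCap database", and places this after the patient has been included. The material taken from the file includes "former colonoscopies and polypectomies and the pathology report on adenomas resected".
- **Scenario 1**: after the colonoscopy the endoscopist considers the inclusion and exclusion criteria. The patient has at least 48 hours to decide and then returns to receive juice. No pathology check is named in between.
- **Scenario 2**: the patient brings the signed consent "When they come back to the specialized unit for resection, earliest 48 hours after the first colonoscopy", and "If the patients agrees entering the study, they will be handed out 8 liters of carrot juice, diary and questionnaire".
- **Design of the intervention** and **Common pathway**: the only stated reason for removing a patient after inclusion is non-compliance.

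**The concern.** Adenoma is a histological diagnosis, whereas a polyp over 20 mm is an endoscopic finding. One section defines eligibility by the first and another invites on the second, with the pathology report held back until the patient is in the trial. A site that follows the protocol as written will therefore randomise some patients who fail its first inclusion criterion, and the protocol gives them no stated path.

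Three things are at stake:

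- A patient with no excised adenoma cannot contribute to the recurrence of an excised adenoma, which is the first half of the primary aim.
- A patient whose lesion proves malignant may leave the one-year schedule, which would add a missing outcome.
- The randomised population would not be the one named in the aim. If staff drop such patients later without a rule fixed in advance, those are unplanned exclusions after randomisation.

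**Working it through.** **Step 1: the texts side by side.**

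| Question | Protocol text | Section |
|---|---|---|
| What must the lesion be? | Adenoma over 20 mm | Inclusion criteria |
| Who is invited? | Anyone with a polyp over 20 mm | Information collected from patient files |
| When is pathology consulted? | With the rest of the record, after inclusion | Information collected from patient files |
| When is juice handed out? | Scenario 1: at a later visit, no pathology check named. Scenario 2: at the resection visit | Scenarios 1 and 2 |
| Who screens before entry? | The endoscopist, against the criteria | Patient recruitment; Scenario 1 |

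In Scenario 2 the resected specimen cannot have been read when juice is given out. A biopsy from the first colonoscopy might exist, but none is required. In Scenario 1 the report could be available when the patient returns, but nothing asks for it.

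**Step 2: inputs for the size.** From Sample size: recurrence rate 40%; reduction of 20 points, described as 50% relative, hence 40% versus 20%; two-sided chi-square test; 80% power; 400 patients, 1:1; 20% drop-out. Alpha is not stated and 0.05 is assumed. The share *f* of randomised patients without an index adenoma is not in the documents; 5 to 20% is an assumption.

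**Step 3: the protocol's own figure.** With 40% versus 20%, two-sided alpha 0.05 and 80% power, the normal-approximation formula without continuity correction gives 82 per arm, 164 in total. The stated minimum is 328 completers, which is 2 × 164. The stated figure is therefore not reproduced. That is a separate matter, and the present point does not depend on it.

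**Step 4: affected patients contribute nothing.**

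Power = Φ{[d − 1.96 √(2 p̄(1 − p̄)/n)] / √([p₁(1 − p₁) + p₂(1 − p₂)]/n)}, with *n* per arm, d = p₁ − p₂ and p̄ the mean of p₁ and p₂.

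Completers: 400 × 0.80 = 320, or 160 per arm. With p₁ = 0.40, p₂ = 0.20, p̄ = 0.30:

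| *f* | Randomised patients affected | Completers left | Per arm | Power |
|---|---|---|---|---|
| 0 | 0 | 320 | 160 | 97.7% |
| 5% | 0.05 × 400 = 20 | 320 × 0.95 = 304 | 152 | 97.1% |
| 20% | 0.20 × 400 = 80 | 320 × 0.80 = 256 | 128 | 94.2% |

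**Step 5: affected patients stay in, with the same 40% rate in both arms and no benefit** (also an assumption). The active-arm rate becomes 0.20(1 − f) + 0.40f and the contrast shrinks to 20(1 − f) points. At 160 per arm:

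| *f* | Active-arm rate | Contrast | Power |
|---|---|---|---|
| 5% | 0.21 | 19 points | 96.2% |
| 20% | 0.24 | 16 points | 87.0% |

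Both calculations use the proportion with recurrence, because that is what the sample-size section uses. They do not describe the combined number-by-size endpoint.

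**The case against.** The best defence is that the invitation sentence sits in a data-handling section. Read in full, it says that researchers will not open journals before inclusion; it does not set out to replace the eligibility criteria. Patient recruitment refers back to those criteria, and Scenario 1 has the endoscopist apply them. This stands in part. A reader might infer that patients are admitted on size alone, and the documents do not support that: the endoscopist's judgement is a stated screen. But that judgement is visual, and no step confirms it.

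Three other strong readings also go too far.

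- **Such patients are bound to be analysed.** The protocol is silent on this, but analysis sets commonly belong to a statistical analysis plan, which is not at hand. The contradiction about who may enter, and when that is confirmed, belongs to the protocol and does not depend on such a plan.
- **Such patients have no usable outcome.** The Aim also covers metachronous adenomas, and Outcome measures counts the number and size of polyps at one year. A patient with a non-adenomatous index lesion can still contribute to both. That cancer patients would miss the one-year colonoscopy is plausible but not stated.
- **The comparison is biased, or the trial loses its power.** Index histology is settled independently of arm, so randomising before it is read does not bias the comparison. On the protocol's own contrast, power stays above 80% in every case computed here.

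**Conclusion.** The contradiction is real. Eligibility is written in terms of adenoma, invitation in terms of polyp, and the route to enrolment does not require pathology in either scenario and, in Scenario 2, cannot include that of the resected specimen. Some randomised patients would fail criterion 1.

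The consequence is a diluted recurrence component, possible extra missing outcomes and a mismatch between the population and the aim; it is not bias between arms. How many patients are affected cannot be known from the documents. For an assumed 5 to 20%, power at 40% versus 20% falls from about 98% to 97-94% if they contribute nothing, and to 96-87% if they stay in with an unchanged 40% rate. These figures rest on an assumed two-sided alpha of 0.05 and on the protocol's large expected effect. The case for a change therefore rests on the conflicting entry rules and not on lost power.

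**What to change.** Reconcile Inclusion criteria, Patient recruitment, Scenarios 1 and 2, and the section on information collected from patient files, so that they give one entry rule.

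**Preferred:** state that the index pathology report is checked and confirms an adenoma before randomisation and first juice. In Scenario 1 the patient already returns at a later visit. The cost is a short wait, and in Scenario 2 juice could no longer be handed out at the resection visit. The data-handling section would also have to permit this one look at the record before inclusion.

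**If early inclusion is kept:** redefine criterion 1 by size and endoscopic appearance, and align the wording of the aim. Keep all randomised patients in the primary analysis. Pre-specify a further analysis restricted to patients whose index specimen, taken before first juice and read blind to arm, is an adenoma. A primary analysis that drops patients after randomisation is harder to defend, so the restricted analysis should be supportive. This route costs only wording, because the pathology report is already collected, but it accepts some dilution.

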# Patient information from patient journals

To investigate if carrot juice has an effect on polyps we need some information from the patient journal. Research responsible will get this information from the patient journals and entered into the RedCap database.

Patient journal information:

- Pathology results
- Endoscopy results
- Previous cancers
- Past colonoscopies
- Name
- Age
- Gender
- Height
- Weight
- Social Security Number (CPR in Danish context)

We require the information to analyze the identified polyps to compare them with the control follow-up. Age, gender, height, and weight will be used for comparisons and correlations. Name and CPR (Central Person Register - Danish identification number) are needed for patient registration for further anonymization.

# Data retention, storage, destruction and publication

All data will be stored in the electronic database REDCap via OPEN on password-protected computers. All electronic data will be backed up and stored electronically in password secured computers. All paper data will be archived and stored in a locked cabinet in the Research Office of the Department of Surgery, OUH. Data retrieved from EPJ is transferred to the RedCap database directly. Data is stored securely in the RedCap database for 5 years (until 31 December 2028), after which will either be destroyed or transferred to the National Archives.

Additionally, we plan to publish the findings in a peer-reviewed journal. Participant anonymity and confidentiality will be preserved as only aggregated findings will be presented or reported. In case of data breach, the incident will be reported to Datatilsynet and the affected participants will be informed.

The Data Protection Regulation and the Data Protection Act are complied. The project is registered with the Data Protection Agency before the start of the project.

# Product - carrot juice and placebo

The cultivation of "Yellowstone" carrots will be conducted by DanRoots A/S.DanRoots, Organic Vegetables, Bjerringbro, Denmark. For each kg of carrots, 800 ml of juice can be extracted. There will be some waist by distributing the juice and placebo to four different locations. We have ordered 7.5 tons carrots for delivery November 1th 2023 and 7,5 tons carrots by November 1th 2024.

Juice is produced and taste corrected by Orskov Food, Denmark in collaboration with Naturfrisk, Ørbæk. The test is corrected to prevent enabling differentiation between carrot juice and placebo.

Analysis of carrot juice for falcarinol and falcarindiol content will be done at random from 10 samples leaving the factory and 10 samples collected after 30 days storage at participant's homes for each batch.

All laboratory investigations are performed at the Dept. of Biochemestry, Svendborg Hospital.

# **Ethics:**

Participation is voluntary with no economic compensation, and the patients are informed orally and in writing according to the information accepted by the ethics committee. They will be given at least 48 hours to consider participation. As the study is structured as a two-armed trial wherein one group will receive active carrot juice while the other will receive a placebo drink, there is no guarantee of patient benefit from participation. The effectiveness of the active carrot juice is not assured, and this is the principal focus of investigation within the study. However, patients are invited to participate due to the potential of specific carrot compounds and their hypothesized capacity to reduce cancer risk.

There are no known side effects to the consumption of carrot juice in the used amount. The lowest toxic dose giving side effects is > 20 times higher than the one offered (10). Meta analyses have demonstrated that a high consumption of carrots is correlated to a reduced mortality risk (1,5). The juice and placebo has been used in an earlier trial with the permission from the Ethics committee (your journal number 21/60480) with no observed side effects.

The deviation from standard follow-up periods is believed to cause no, or very little additional risk to patients. Some Swedish patients are investigated 1-2 years earlier and some Danish patients 3 to 6 months earlier.

It is our judgement that the potential gain by producing evidence for at effective prophylaxis against colorectal neoplasia and likely cancer by large outweighs the theoretical side effects and disadvantages of the trial.

Approval from the ethical committee has not yet been obtained but is considered to cause no problem. The National Danish Drugs Administration has been consulted and the trial is not considered to be a drug-trial and is not under the GCP regulations and can therefore be initiated without their approval. The project is registered internally to the Region of Southern Denmark (intern fortegnelse over forskningsprojekter).

Patients are covered by the Patient Insurance (patientforsikringen) in Denmark and the "patientförsäkring" in Sweden.

# **Economy**:

The study is investigator initiated. Our commercial partners have provided carrots and juice for free and at reduced prizes. No money has been payed by commercial companies. The foundation: Sygeforsikringen "danmark" has donated 5 mio dkk to the condition of the trial. (budget attached). No project member have personal benefit besides their regular salary by the participation and no economic interests in any of the commercial partner companies. The grant is managed by "Forskerservice". The hospital economy department at Odense University Hospital and the account is subject to public revision. The study hasn't received any other funding.

There will be no compensation to trial participants.

# Time schedule:

The clinical studies:

Protocol for the Px7 trial will be finished before October 1'th 2023, including approval from the ethical committee and the data protection agency.

Database and electronic randomization algorithm will be ready before October 1'th 2023

Experiments with placebo juice ended before October 2023. For effective inactivation and taste adjustments.

Planting carrots will be ordered in March 2023 (done) and harvested in October 2023 and October 2024

Contract on juice production before July 2023 (done)

Questionnaires for patients will be finished before December 2023.

Inclusion of patients into the px7 trial will await the 2023 carrot harvest. It can be initiated November 2023. Inclusion will take 12 month, and observation until follow up colonoscopy will be ended January 2026.

Publications will be produced before January 2027.

### **Publication plan:**

The protocol will be published in Clinical Trials.com or a similar journal.

The results will be published at clinicaltrials.gov or clinicaltrialregister.eu, the results will be published regardless of they are positive, negative or inconclusive for the study.

The main paper and all spin off papers will be published in international open access journals. Vancouver rules will be followed when deciding authors. Both positive and negative results will be published.

The communication co-worker [name], The Surgical research Unit, OUH on the project will timely inform the press and other public actors to achieve maximal national coverage for the general population.

Budget: Attached as a separate file.

